16.5.6 Forest plots for biomarker and non-biomarker subgroups

Forest plots for the ORR, the CR rate, and the hazard ratio between the subgroups of a particular subgroup factor (determined from a univariable Cox regression model) will be

produced for the biomarker and non-biomarker subgroups as defined in Sections 10.12, 10.10, and 11.4. The plots will be based on the FAS and generated separately for both the IRC and INV response assessment.

16.5.7 ASCT ineligibility subgroups

Subgroup analyses

In addition to the ASCT ineligibility subgroups as defined in Section 8.6.3, the following four mutually exclusive categories will be defined:

- **Chemorefractory patients:**
 - Chemorefractory patients as indicated on the eCRF page 'ASCT Ineligibility Criteria' ('Failure to achieve PR or CR with salvage therapy').
 - Patients who underwent a stem cell transplantation before as indicated on the eCRF page 'Prior Cancer Therapies for DLBCL – Autologous Stem Cell Transplants'.
 - The presence or absence of any other reason such as comorbidities or high age will be ignored.
- **Co-morbid patients**
 - Only those patients will be considered who are *not* already in the 'Chemorefractory' group.
 - Co-morbid as indicated on the 'ASCT Ineligibility Criteria' page
 - Presence or absence of other reasons such as high age will be ignored.
- **Patients of high age**
 - Only those patients will be considered who are *not* already in the 'Chemorefractory' or 'co-morbid' category.
 - All patients who are ineligible due to high age as indicated on the eCRF page 'ASCT Ineligibility Criteria' ('Age > 70 years'). Other reasons for ASCT ineligibility like 'Refusal' or 'Other reasons' will be ignored.
- **Refusal**
 - Only those patients will be considered who are not already in the 'Chemorefractory', 'Co-morbid', or 'High age' category.
 - All patients who are ineligible due to the patients' refusal to undergo ASCT as indicated on the eCRF page 'ASCT Ineligibility Criteria'.
- **Other reasons**

STATISTICAL ANALYSIS PLAN

 MorphoSys AG
 MOR208C203

- All other patients who are not in the categories above will be considered as ASCT ineligible due to other reasons.

Table 16: Reasons for ASCT Ineligibility

Priority	High level category	Reason from eCRF
1	Chemorefractory	Failure to achieve PR or CR with salvage therapy
		Prior ASCT as indicated in eCRF page 'Prior Cancer Therapies for DLBCL – Autologous Stem Cell Transplants'
2	Comorbidity	Diffusion lung capacity for carbon monoxide <50% by pulmonary function test
		Left ventricular ejection fraction <50% by multiple gated acquisition echocardiogram
		Other organ dysfunction or comorbidities precluding the use of HDT/ASCT on the basis of unacceptable risk of treatment
3	Age	Age >70 years
4	Refusal	Patient refusal of HDT/ASCT
5	Other	Other Reason

The reasons for being ASCT ineligible will be summarized for the FAS. The following subgroup analyses in terms of efficacy will be conducted based on both the INV and IRC response assessment (using the FAS):

- PFS
- OS
- DoR

-
- ORR

Both Tables and Kaplan-Meier curves for time-to-event analyses will be produced as described in the respective sections that detail the analysis of the listed endpoints. If less than three patients are included in the 'Other' category this subgroup will not be analyzed or displayed in the graphs.

Contingency table for displaying the reasons for ASCT ineligibility

The five reasons for being ASCT ineligible as defined above are presented in a cross-table. The table will show the number of patients who are characterized by a particular combination of two different ASCT ineligibility reasons. For this summary the reasons for ASCT ineligibility are not defined as mutually exclusive, i.e, a patient can have more than one reason for being ASCT ineligible, resulting in the fact that patients can generally be represented multiple times in the table. Percentages are calculated row-wise and are based on the number of patients in FAS with reason for ASCT ineligibility as displayed in the first column.

The contingency table will be produced for:

- The FAS
- The subgroup of patients with only one prior treatment line (on the FAS)
- The subgroup of patients with two prior treatment lines (on the FAS)
- The subgroup of patients with three or four prior treatment lines (on the FAS)

16.5.8 NK cell numbers at baseline

In analogy to the subgroup analysis specified in Section 10.12 the NK cell categories are additionally defined using a cut-off of 100 NK cells/ μ l (<100 cells/ μ l vs. \geq 100 cells/ μ l). The following efficacy analyses will be conducted based on the FAS:

- PFS (based on IRC only)
- OS
- ORR (based on IRC only)
- DoR (based on IRC only)

Kaplan-Meier curves will be produced for time-to-event endpoints.

Baseline characteristics in the NK count subgroups defined by the cut-off of 100 NK cells/ μ l will be tabulated as described in Section 8.5.

16.5.9 Swimmers plot for responders

A swimmers plot will be produced for the responders in the FAS. The bar length will indicate the time on treatment defined as follows: (date end of treatment – date of first dosing with any study drug) + 1. Different landmarks will be indicated in the plot:

- Arrow heads: indicate if a patient is still ongoing on treatment at data cut-off.
- Patients who have discontinued treatment are indicated by a blunt end of the bar.
- Time to partial response and time to complete response is indicated by different symbols.
- A symbol at the start of the bar will indicate if a patient is primary refractory.
- A symbol at the end of the bar will indicate if a patient has already progressed.

17. SAP ADDENDUM 2.0

17.1 Efficacy in subgroups of BCL-2 expression levels determined by IHC

Three complementary subgroups of patients will be defined:

- Patients with high BCL-2 expression: $\geq 50\%$ BCL-2-positive cells and BCL-2 staining intensity ≥ 2
- Patients with low BCL-2 expression:
 - $< 50\%$ BCL-2-positive cells and BCL-2 staining intensity < 2
 - $< 50\%$ BCL-2-positive cells, and BCL-2 staining intensity ≥ 2 or unknown staining intensity
 - BCL-2 staining intensity < 2 , and $\geq 50\%$ BCL-2-positive cells or unknown percentage of positive cells
- Patients with unknown status regarding BCL-2 expression:
 - $\geq 50\%$ BCL-2-positive cells and unknown BCL-2 staining intensity
 - BCL-2 staining intensity ≥ 2 and unknown percentage of BCL-2 positive cells
 - Unknown percentage of BCL-2 positive cells, and unknown BCL-2 staining intensity

The following endpoints will be summarized for the BCL-2 subgroups based on the FAS:

- ORR (based on IRC only)
- PFS (based on IRC only)
- DoR (based on IRC only)
- OS

The methodology for summarizing the endpoints are described in Sections 9, 10.2, 10.3, and 10.4. Kaplan-Meier plots will be presented for the time-to-event endpoints.

17.2 Efficacy in alternative age subgroups

In addition to the subgroup analysis specified in Section 16.5.4, selected efficacy endpoints will also be analyzed for the following subgroups:

- Patients of ≤ 65 years of age
- Patients of > 65 years of age

The following endpoints will be summarized for the alternative age subgroups based on the FAS:

- ORR (based on IRC only)
- PFS (based on IRC only)
- DoR (based on IRC only)
- OS

The methodology for summarizing the endpoints are described in Sections 9, 10.2, 10.3, and 10.4. Kaplan-Meier plots will be presented for the time-to-event endpoints.

17.3 Efficacy in different histological subgroups

Selected endpoints will be reported for patients belonging to different pathological subgroups as per central pathology are depicted in Table 17. Pathological subgroups will be identified as outlined in Section 17.8. Moreover, the duration of being progression-free will be visualized in a swimmer plot. Summaries will be generated based on the FAS.

Table 17: Analyses for various NHL subgroups as per central pathology

Histology	Outputs
DLBCL, no further specification	ORR, (CR rate, PR rate) DoR PFS OS Swimmer plot
Composite Lymphoma with DLBCL Component	ORR, (CR rate, PR rate) DoR PFS OS Swimmer plot
Any high grade lymphoma with double or triple hit	ORR, (CR rate, PR rate) Swimmer plot
EBV positive DLBCL + T cell histiocyte-rich large B cell lymphoma	ORR, (CR rate, PR rate) Swimmer plot
Follicular Lymphoma Grade 2 ± Grade 3A	ORR, (CR rate, PR rate) Swimmer plot
Mantle Cell Lymphoma	ORR, (CR rate, PR rate) Swimmer plot
Marginal Zone Lymphoma	ORR, (CR rate, PR rate) DoR Swimmer plot

STATISTICAL ANALYSIS PLAN

 MorphoSys AG
 MOR208C203

Histological transformation to DLBCL from indolent NHL	ORR, (CR rate, PR rate) Swimmers plot
Unknown / missing	ORR, (CR rate, PR rate) Swimmers plot

The methodology for summarizing the endpoints ORR, DoR, PFS, and OS are described in Sections 9, 10.2, 10.3, and 10.4.

The swimmer plot will be designed as follows:

- the length of the bar will indicate the time of being progression free in months.
- a blunt end indicates progression
- an arrow head will indicate that the patient is still progression-free: color-coding for the arrow head will be used to indicate if the patient is still ongoing on PFS-follow-up, or has been censored due to other reasons
- bars will be color-coded to differentiate between patients with PR and CR as best response
- the patient ID will be shown for each bar, together with the number of prior treatment lines
- symbols will be used to indicate the point in time (relative to first dosing with any study drug) when the first PR and first CR was detected
- symbols on the right of the bars will be used to indicate if a patient is primary refractory and/or refractory to his/her last prior treatment line Best response and progression free survival will be based on the IRC evaluation.

17.4 Identification of transformed lymphoma patients

Section 8.6.4 describes how patients with previous indolent lymphoma (i.e., patients who transformed to high-grade lymphoma) are identified. The algorithm will be modified as follows:

- “Presumed INHL” will be added to the list of search terms.
- Patients who developed a secondary indolent lymphoma after the diagnosis of DLBCL (or other high-grade lymphoma as specified in the protocol) will not be considered.
- Patients who have the reference diagnosis “HISTOLOGICAL TRANSFORMATION TO DLBCL FROM INDOLENT NHL” per central pathology assessment will also be considered.

17.5 Swimmer plot for patients with transformed lymphoma

A swimmer plot for patients with transformed lymphoma will be produced. The strategy to identify patients with previously indolent lymphoma that had transformed to a high-grade lymphoma is outlined in Sections 8.6.4 and 17.4.

The swimmer plot will be produced as described in Section 17.3

17.6 Deaths

Section 10.7.3.1.6 describes how deaths will be summarized according to the following categories: PD-related vs. non-PD-related. The list of terms determining that a death is PD-related will be extended by the terms “Progression”, “Study disease” and “Progression of the disease”. The following terms will lead to a classification into the new “Unknown” category in terms of PD-relatedness:

- “End stage marrow failure”
- “Unkown”

In case that for a patient more than one cause of death is reported in different sections of the eCRF, the patients’s death will be categorized as PD-related if at least one of the causes of death is classified as PD-related.

17.7 Lenalidomide dose intensity

The dose intensity is calculated as average daily dose of treatment.

$$\text{Dose Intensity (mg/day)} = \frac{\text{Cumulative dose (mg)}}{\text{Duration of exposure (days)}}$$

While considering treatment duration, discontinuation for any reason (disease progression, AE, Investigator’s decision, etc) will be taken into account.

A total daily dose will be multiplied with the difference between the “dosing stop study day” and the “dosing start study day” + 1 for each cycle. Days where no Lenalidomide capsule is taken are counted as days with a dose of 0 mg. The difference in number of capsules dispensed and returned will not be considered.

Exemplified calculation:

Dosing start day	Dosing end day	Total daily dose (mg)	Total dose (mg)
1	21	25	25 x 21 = 525

STATISTICAL ANALYSIS PLAN

 MorphoSys AG
 MOR208C203

30	50	25	25 x 21 = 525
59	79	20	20 x 21 = 420
87	91	10	10 x 5 = 50
Dose intensity = (525 + 525 + 420 + 50) / 91 = 16.7 mg			

Dose intensity of Lenalidomide will be summarized based on the FAS.

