8.2 Enrolled patients

The following summaries will be provided: % based on the total number of Enrolled patients:

- Number (%) of patients who were treated with study drug (split by MOR00208, LEN, and both study drugs).
- Number (%) of patients who are still on-treatment with study drug split MOR00208, LEN, both drugs, or any drug (all Cycles considered; only for the primary analysis).
- Number (%) of patients who are ongoing with combination treatment (Cycles 1-12).
- Number (%) of patients who discontinued *only* one of the two study drugs (split by LEN only, MOR00208 only), or *both* study drugs during combination treatment (Cycle 1 to 12) including the primary reason for discontinuation. The discontinuation of LEN as per protocol after Cycle 12 will not be considered here. If drugs are sequentially discontinued, the reason for discontinuation of the later drug will be reported as reason for the discontinuation of both drugs.
- Number (%) of patients who discontinued MOR00208 or LEN before completing 12 Cycles. All discontinuations are considered including both the discontinuation of MOR00208/LEN *only* or a sequential discontinuation of both drugs. The reason for discontinuation will also be reported.
- Number (%) of patients who *successfully* completed combination treatment (Cycles 1- 12), i.e., patients who completed 12 Cycles on *both* drugs.
- Number (%) of patients who reached Cycle 13 Day 1 on at least one study drug (split by both drugs, LEN only, MOR00208 only, any study drug).

**STATISTICAL ANALYSIS PLAN**MorphoSys AG
MOR208C203

-
- Number (%) of patients who are still ongoing with MOR00208 only, LEN only, or both drugs after completion of Cycle 12 (i.e., ongoing from Cycles 13 onwards; only for primary analysis).
 - Number (%) of patients who discontinued MOR00208 beyond Cycle 12 regardless of successful or unsuccessful completion of the combination treatment phase, including the reason for discontinuation.
 - Number (%) of patients who discontinued MOR00208 after *successful* completion of combination treatment phase (Cycle 1-12) including the reason for discontinuation. Successful completion means that the patient completed 12 Cycles on combination treatment.
 - Number (%) of patients who discontinued LEN after completion of the combination treatment (Cycle 1 to 12) including the reason for discontinuation (e.g., completion as per protocol).

NOTES:

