8.9.2 Exposure

6.1.1 Duration of exposure to study drug

Exposure to study treatment and each study drug will be summarized for the FAS and the SAF.

Duration of exposure (days) = (last date of exposure to study drug) – (date of first administration of study drug) + 1.

Taking into account the period of rest between infusions, the **last date of exposure** is defined as follows:

- For MOR00208: When the study drug is administered over several regular doses with regular time intervals, the last date of exposure is identified according to the planned dose schedule of the cycle. If no rest period is included in the cycle then the last date of exposure is: (last date of administration of the study drug) + (length of time interval-1). **Length of time interval:** 7 days in Cycle 1-3 and 14 days from Cycle 4 onwards. In case a patient dies before the end of the time interval the date of death will be used to truncate the time interval, i.e., in this case the last date of exposure will be set as the date of death.
- For LEN, the last date of exposure will be defined as the last date of administration. Thus, planned dose interruptions between days 22 to 28 of each cycle, as per protocol, will not be considered. That is, only day 1 to 21 will be considered as being exposed to LEN.

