9.1.1 Exposure analysis

- The number of patients completing each cycle will be summarized. A patient is considered to have completed a cycle for MOR00208 if he/she was compliant for all MOR00208 infusions during the cycle. A patient is considered to have completed a cycle for LEN if he/she was compliant (see Section 8.9.6) for LEN administration during the cycle.
- Summary statistics will be displayed. The duration of exposure will also be summarized according to the following categories: Month 1-2, 3-4, 5-6, 7-8, etc.
- Number of infusions with MOR00208 will be summarized as follows:
 - The total number of MOR00208 infusions will be summarized
 - The number (%) of patients belonging to the following categories will be derived: 0-2 infusions, 3-4 infusions, 5-6 infusions, 7-8 infusions, etc.

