11.1.1 LEN

LEN is taken for the first 21 days of each cycle. Patients experiencing a transient treatment interruption, e.g., due to toxicities, or patients undergoing treatment discontinuation may take LEN for less than 21 days, which would not be considered as non-compliance. Similarly, a planned reduction of the *Total Daily Dose* will not be considered as non-compliance.

For some patients and Cycles the *Total Daily Dose* will be reached by combining tablets of two different *Dose Strengths*. Compliance will be calculated as follows:

If $(\text{total used dose})/(\text{total planned dose})$ is between 80% and 120%, both inclusive, of the assigned dosage during a particular cycle, then the patient is considered compliant for LEN during that particular cycle. The *Total Planned Dose* and the *Total Used Dose* will be derived as follows:

For patients who did not experience a dose change or treatment interruption (as indicated on the eCRF page '*Lenalidomide Dosing Record*):

- The **Total Planned Dose** will be calculated as follows:
 $21 \times \text{Total Daily Dose}$ (as entered on the eCRF page '*Lenalidomide Dosing Record*').
- The **Total Used Dose** will be calculated as follows:
 - For patients and cycles in which the Total Daily Dose is reached by taking one capsule only:

STATISTICAL ANALYSIS PLAN

 MorphoSys AG
 MOR208C203

Total Used Dose = (Number of Capsules Dispensed - Number of Capsules Returned) x Dose Strength.

For patients and cycles in which the Total Daily Dose is reached by combining two or more capsules of different Dose Strengths (e.g., Dose Strength 1 and Dose Strength 2):

Total Used Dose = [(Number of Capsules of Dose Strength 1 Dispensed - Number of Capsules of Dose Strength 1 Returned) x Dose Strength 1] + [(Number of Capsules of Dose Strength 2 Dispensed - Number of Capsules of Dose Strength 2 Returned) x Dose Strength 2].

For patients who experienced a dose change, treatment interruption or treatment discontinuation (as indicated on the eCRF page '*Lenalidomide Dosing Record*'):

- The **Total Planned Dose** will be calculated as follows:
 - Patients who required a dose change or interruption and did not start LEN treatment (with same or changed dose) before completion of that particular Cycle the dose change/interruption happened:

$\text{Min}[21, (\text{Dosing Stop Date} - \text{Dosing Start Date} + 1)] \times \text{Total Daily Dose}$ (as entered on the eCRF page '*Lenalidomide Dosing Record*').

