- Interruption and re-initiation of treatment within a particular Cycle: Capsules of only one dose strength or a combination of several dose strengths might be used to reach the targeted Total Daily Dose. The Total Used Dose will be calculated as follows (e.g., for capsules of two different dose strengths):

$$\begin{aligned} \text{Total Used Dose} = & [\text{Number of Capsules of Dose Strength 1 Dispensed before dose change} \times \text{Dose Strength 1}] + [\text{Number of Capsules of Dose Strength 2 Dispensed before dose change} \times \text{Dose Strength 2}] + \\ & [\text{Number of Capsules of Dose Strength 1 Returned after dose change} \times \text{Dose Strength 1}] + [\text{Number of Capsules of Dose Strength 2 Returned after dose change} \times \text{Dose Strength 2}]. \end{aligned}$$

Notes: The *Total Daily Dose* before and after interruption in a particular Cycle is represented in separate log lines on the eCRF page '*Lenalidomide Dosing Record*'.

- The following applies if the *Total Planned Dose* is 0 for an entire Cycle:

-
- If the **Total Used Dose** is 0 for the Cycle, the patient will be considered as compliant for that particular Cycle.
 - If the **Total Used Dose** is not 0, the patient will be considered as non-compliant for that particular Cycle.

Listings showing eCRF entries on LEN dosing records, MOR00208 dosing administration, and MOR00208 infusion details will be produced (for the SAF). A listing will be generated showing the compliance per cycle for each individual for both LEN and MOR00208 (for the SAF).

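### The SAP counts LEN cycles that were cut short or wholly held as completed; separately, its LEN dose-intensity figure is not comparable across treatment durations

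*SAP*

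**What the plan says.** **Completed cycles.** SAP 8.9.2, under Exposure analysis, tabulates how many patients complete each cycle. For LEN the definition is: "A patient is considered to have completed a cycle for LEN if he/she was compliant". It refers to SAP 8.9.6 for compliance.

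**Compliance.** SAP 8.9.6 compares used with planned dose in each cycle and accepts 80% to 120%. Patients who interrupt or discontinue LEN "may take LEN for less than 21 days, which would not be considered as non-compliance". If LEN is not restarted within the cycle, the planned dose is the smaller of 21 and the number of days from dosing start to dosing stop, times the daily dose. When the planned dose for a whole cycle is zero and the used dose "is 0 for the Cycle, the patient will be considered as compliant for that particular Cycle".

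**Twelve-cycle completion.** SAP 8.2 reports patients who successfully "completed combination treatment (Cycles 1- 12), i.e., patients who completed 12 Cycles on" both drugs. It does not define a completed cycle or cite 8.9.6.

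**Dose intensity.** SAP 17.7 states: "The dose intensity is calculated as average daily dose of treatment". It is cumulative dose over duration of exposure. "While considering treatment duration, discontinuation for any reason (disease progression, AE, Investigator’s decision, etc) will be taken into account", and "Days where no Lenalidomide capsule is taken are counted as days with a dose of 0 mg". The worked example gives 16.7 mg from 1520 mg over 91 days. SAP 8.9.2 ends LEN exposure at the last administration and adds: "That is, only day 1 to 21 will be considered as being exposed to LEN".

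**The concern.** Compliance asks whether the patient did what was instructed. Completion asks whether the cycle was delivered. Not penalising a patient who follows an instruction to hold LEN is right for the first question and wrong for the second. If one definition serves both, the cycles that toxicity cut short or removed are the ones reported as delivered, and a reader would take the table as evidence that LEN was better tolerated than it was.

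The dose-intensity measure has a different weakness. The SAP's list of changes says it was added as relevant to interpreting both efficacy and safety. A patient who took every capsule for a year should not score below one who stopped after a few days, yet that is how the definition ranks them.

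**Working it through.** **1. Completion, from SAP 8.9.2 and 8.9.6.** Assume 25 mg daily and that all unused capsules are returned, so that used dose equals dose taken.

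- Stop on Day 3, no restart: planned = min(21, 3) x 25 = 75 mg; used = 75 mg; ratio 100%, so compliant and completed. Against a full cycle of 21 x 25 = 525 mg the patient received 75/525 = 14.3%.
- Stop on Day 5, no restart: planned 125 mg, used 125 mg, ratio 100%, so completed. Against 525 mg: 23.8%.
- Held for the whole cycle: planned 0, used 0, so compliant by rule and completed. Against 525 mg: 0%.

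With a threshold of 80% of scheduled days, 0.8 x 21 = 16.8, so 17 days are needed. Cycles with 0 to 16 LEN days can count as completed today and would not count then.

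**2. The SAP 17.7 example.** The dosing records are Days 1-21 and 30-50 at 25 mg, 59-79 at 20 mg and 87-91 at 10 mg.

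- Cumulative dose: 525 + 525 + 420 + 50 = 1520 mg.
- Days from first to last dose: 91 - 1 + 1 = 91.
- 1520/91 = 16.7 mg/day, which reproduces the SAP's figure.
- Counting dosing days only gives 1520/68 = 22.4, which does not. The SAP therefore counts the days between dosing periods as 0 mg and stops the clock at the last dose.

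**3. Full 25 mg dosing over k undelayed cycles.** SAP 8.9.1 gives 28-day cycles with LEN on Days 1-21. The 17.7 value is 525k / (28(k - 1) + 21). With the clock run to the end of the last started cycle it is 525k / 28k.

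| Cycles | SAP 17.7 (mg/day) | Clock to cycle end (mg/day) |
|---|---|---|
| 1 | 525/21 = 25.0 | 525/28 = 18.75 |
| 2 | 1050/49 = 21.4 | 1050/56 = 18.75 |
| 3 | 1575/77 = 20.5 | 1575/84 = 18.75 |
| 6 | 3150/161 = 19.6 | 3150/168 = 18.75 |
| 12 | 6300/329 = 19.1 | 6300/336 = 18.75 |

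The fall from one cycle to twelve is about 23% with no dose missed; from three to twelve it is about 6%. A patient who stops on Day 5 scores 125/5 = 25.0 under 17.7, above the patient who took all 6300 mg. With the clock run to the cycle end, the Day-5 patient scores 125/28 = 4.5.

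**The case against.** The best defence is that other tables show what these two obscure. SAP 16.2 gives LEN relative dose intensity by cycle against a fixed 525 mg. SAP 20.5.1 compares cumulative LEN with a full-dose reference. Reductions, interruptions and permanent discontinuations are tabulated in 8.9.3 to 8.9.5, interruptions again in 16.3.4, and LEN discontinuation before 12 cycles with its reason in 8.2. The Day-3 stop would be visible there. This stands as a limit on the consequence: a distorted overall tolerability conclusion is not shown. It does not correct the completion count or the 17.7 values. SAP 16.2 is also not a clean substitute as printed, since it writes the pill count as returned minus dispensed.

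Three stronger readings of 17.7 are tempting, and the documents do not support them.

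- *An arithmetic error in the worked example.* There is none; 1520/91 is 16.7.
- *A contradiction with 8.9.2.* The duration formula there, last LEN date minus first plus one, gives the same 91 days. The sentence limiting exposure to Days 1 to 21 sits in the definition of the last exposure date and most naturally means that no trailing rest week is added. It is loosely worded, not clearly contradictory.
- *A favourable bias.* Against a nominal 25 mg/day, 17.7 understates full dosing for anyone with two or more cycles. The net effect on a pooled mean depends on the mix of durations, which the documents do not give.

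A calendar denominator also has a merit worth keeping. Protocol 6.6.2 delays a new cycle until toxicity resolves, and calendar days capture that delay. Dividing by 21 days per started cycle would lose it.

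**Conclusion.** **Completion: wrong as written.** The three provisions together make cycles cut short or wholly held count as completed, so the count errs in one direction, upwards. The size cannot be computed, because the documents do not say how many cycles are affected. If about 80 patients form the denominator, each affected patient adds 1/80 = 1.25 percentage points in that cycle. The SAP does not say whether cycles after permanent LEN discontinuation are also scored as zero planned and zero used; if they are, the overstatement grows in later cycles.

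A reader might infer that the 12-cycle completion figure in SAP 8.2 is overstated too. That holds only if 8.2 borrows the 8.9.2 definition. It does not say so, and its notes rely on the End of Treatment page and on reaching Cycle 13.

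**Dose intensity: a real but secondary artefact.** Values are not comparable between patients with different LEN durations. The gap for perfect dosing is at most 25.0 against 19.1 mg/day and depends mainly on very short treatment. No direction of bias is established.

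Both summaries are descriptive, and the primary ORR analysis is unaffected.

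**What to change.** **SAP 8.9.2 and 8.2.** Separate completion from compliance.

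- Count a LEN cycle as completed only if LEN was taken on a stated minimum share of the 21 scheduled days, for example 80% (17 days), at whatever dose level was assigned.
- Count a cycle with no LEN as not completed, and say how cycles after permanent discontinuation are treated.
- Keep 8.9.6 for compliance only.
- State in 8.2 that 12 cycles on both drugs uses the completion definition.

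**SAP 17.7.** Keep calendar days, so that cycle delays still count, but run the clock to the end of the last started 28-day cycle, and amend the sentence on discontinuation to match. Update the worked example to the new definition: if the fourth cycle starts on Day 87 it ends on Day 114, and 1520/114 = 13.3 mg/day. In 8.9.2, make clear that the Days 1 to 21 sentence concerns the exposure end date.

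**Cost.** SAP wording and two derivations, from data already on the Lenalidomide Dosing Record. Reported LEN cycle completion becomes less favourable. Under the revised 17.7 a mid-cycle stop lowers the patient's value, which should be footnoted. The 80% share is a choice to be fixed before the tables are rerun.
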